10.4 APPENDIX 4: ADDITIONAL APPENDICES

Product Name: PRN473 (SAR444727)

10.4.1 Grading of application site tolerability symptoms

Grade	Burning/Stinging	Pruritus	Erythema
0 (none)	No stinging/burning	No pruritus	No detectable erythema; skin of normal color
1 (mild)	Slight warm, tingling sensation; not really bothersome	Occasional, slight itching/scratching	Slight pinkness present
2 (moderate)	Definite warm, tingling sensation that is somewhat bothersome	Constant or intermittent itching/scratching that is not disturbing sleep	Definite redness, easily recognized
3 (severe)	Hot, tingling/stinging sensation that has caused definite discomfort	Bothersome itching/scratching that is disturbing sleep	Intense redness

Adapted from: Zane 2016.

10.4.2 Validated investigator global assessment-atopic dermatitis (vIGA-AD)

Validated Investigator Global Assessment scale for Atopic Dermatitis

vIGA-AD™

Instructions:

Product Name: PRN473 (SAR444727)

The IGA score is selected using the descriptors below that best describe the overall appearance of the lesions at a given time point. It is not necessary that all characteristics under Morphological Description be present.

Score	Morphological Description
0 – Clear	No inflammatory signs of atopic dermatitis (no erythema, no induration/papulation, no lichenification, no oozing/crusting). Post-inflammatory hyperpigmentation and/or hypopigmentation may be present.
1 – Almost clear	Barely perceptible erythema, barely perceptible induration/papulation, and/or minimal lichenification. No oozing or crusting.
2 – Mild	Slight but definite erythema (pink), slight but definite induration/papulation, and/or slight but definite lichenification. No oozing or crusting.
3 – Moderate	Clearly perceptible erythema (dull red), clearly perceptible induration/papulation, and/or clearly perceptible lichenification. Oozing and crusting may be present.
4 – Severe	Marked erythema (deep or bright red), marked induration/papulation, and/or marked lichenification. Disease is widespread in extent. Oozing or crusting may be present.

Notes:

1. In indeterminate cases, please use extent to differentiate between scores.

For example:

- Patient with marked erythema (deep or bright red), marked papulation and/or marked lichenification that
 is limited in extent, will be considered "3 Moderate".
- 2. Excoriations should not be considered when assessing disease severity.

Copyright ©2017 Eli Lilly and Company – Used with the permission of Eli Lilly and Company under a Creative Commons Attribution-NoDerivatives 4.0 International License - https://creativecommons.org/licenses/by-nd/4.0/

10.4.3 Lesion Total Sign Score (TSS)

Product Name: PRN473 (SAR444727)

Scale	Erythema	Induration/Papulation	Excoriation	Lichenification
0 (none)	None	None	None	None
1	Mild	Mild	Mild	Mild
2	Moderate	Moderate	Moderate	Moderate
3	Severe	Severe	Severe	Severe

10.4.4 Hanifin and rajka criteria

The patient must have 3 of the major criteria and 3 of the minor criteria to be eligible for the study.

3 A F		a	•
Mai	or	Crit	eria
MIA	OI.	CIII	

- 1. Pruritus
- 2. Typical morphology and distribution Flexural lichenification in adults
 - Facial and extensor eruptions in infants and children
- 3. Chronic or chronically relapsing dermatitis
- 4. Personal or family history of atopy (asthma, allergic rhinitis, atopic dermatitis)

	Minor Criteria			
1.	Xerosis	12. Keratoconus		
2.	Ichthyosis/palmar hyperlinearity, keratosis pilaris	13. Anterior subcapsular cataracts		
3.	Immediate (type 1) skin-test reactivity	14. Orbital darkening		
4.	Raised serum IgE	15. Facial pallor, facial erythema		
5.	Early age of onset	16. Pityriasis alba		
6.	Tendency toward cutaneous infections (especially Staphylococcus aureus and herpes simplex), impaired cell-mediated immunity	17. Anterior neck folds18. Itch when sweating19. Intolerance to wool and lipid solvents		
7.	Tendency toward non-specific hand or foot dermatitis	20. Perifollicular accentuation 21. Food intolerance		
8.	Nipple eczema	22. Course influenced by environmental or emotional		
9.	Cheilitis	factors		
	Recurrent conjunctivitis Dennie-Morgan infraorbital fold	23. White dermographism, delayed blanch		

Source: Hanifin 1980.

10.5 APPENDIX 5: PROTOCOL AMENDMENT HISTORY

The Protocol Amendment Summary of Changes Table for the current amendment (amended protocol 02) is located directly before the Table of Contents.

Amendment 01 (15 June 2021)

Product Name: PRN473 (SAR444727)

This amended protocol 01 (amendment 01) is considered to be substantial based on the criteria set forth in Article 10(a) of Directive 2001/20/EC of the European Parliament and the Council of the European Union.

OVERALL RATIONALE FOR THE AMENDMENT

This protocol is being amended to incorporate feedback from health authorities as well as other clarifications deemed necessary by the Sponsor.

Protocol amendment summary of changes table

Section # and Name	Description of Change	Brief Rationale
Title Page	Updated protocol version and date.	Administrative.
Protocol amendment summary of changes table	Inserted table to include the document history related to the initial Clinical Study Protocol and the Amended Clinical Study Protocol.	New section per Sanofi protocol template and process.
	Inserted for the current Amended Clinical Study Protocol text related to the overall rationale and protocol amendment summary of changes table.	
Section 1.1 synopsis; Section 4.1 overall design; Section 4.3 justification of dose; Section 5.1 inclusion criteria #7; Section 6.2 Preparation/handling/storage/accountability	Updated the investigational skin lesion from "10*10 cm" to "100cm2"	To provide flexibility for the lesional area.
Section 1.1 synopsis; Section 1.2 schema; Section 4.1 overall design; Section 5.1 inclusion criteria #5,#6; Section 6.7.3 rescue medicine	Added "genital" in the excluded treatable areas for PRN473 Gel administration.	To respond the FDA's comment of considering exclusion of mucosal sites such as the genitalia.
Section 1.1 synopsis; Section 1.2 schema; Section 4.1 overall design	Added the following text to clarify the administration of study intervention during Open Label period "and should continue to treat the assigned areas throughout the Open Label Period."	For clarity.
Section 1.1 synopsis, Section 4.1 overall design	Updated the text from" To evaluate the PK (plasma concentrations) and biomarkers of PRN473, blood samples will be collected throughout the study" to "will be collected at	For clarity.

Section # and Name	Description of Change	Brief Rationale
	study visits accordingly to the SoA (Section 1.3)."	
Section 1.1 synopsis; Section 5.1 inclusion criteria	Replaced the eligibility regarding patient's vIGA-AD score at "screening" instead of "baseline "in inclusion #5	To correct a typo.
	Introduced a new inclusion criterion as "inclusion #8" for male contraception/abstinence requirements. And renumbered the following inclusion criteria.	To introduce the male contraception/abstinence requirements in patient eligibility
	Updated the inclusion #9 with Sanofi common text language on female contraception/abstinence and pregnancy testing requirements following decision tree.	To align with Sanofi common text and safety guidance.
Section 1.1 synopsis; Section 5.2 exclusion criteria	Updated the exclusion #17 of any malignancy history to "History of any malignancy except skin basal cell or squamous cell carcinomas in situ that have been removed and completely resolved at least 5 years ago"	To respond the FDA's comment.
	Introduced a new exclusion criterion for laboratory abnormalities as exclusion #18	To align with Sanofi common text and safety guidance.
	Introduced a new exclusion criterion for QT intervals as exclusion #19	To align with Sanofi common text and safety guidance. To respond the FDA's comment to add subject stopping criteria based on ECG abnormalities.
	Introduced the diagnostic assessments for HIV HBV and HCV as exclusion #20, #21, and #22 respectively.	To align with Sanofi common text and safety guidance. To respond the FDA's comment to obtain HIV test prior to study enrollment.

Section # and Name	Description of Change	Brief Rationale
	Added the exclusion #23 on medical condition of tuberculosis as "Evidence of active or latent tuberculosis (TB) as documented by medical history and examination, chest X-rays (posterior anterior and lateral), and TB testing: either a positive tuberculin skin test (TST; defined as a skin induration ≥ 5 mm at 48 to 72 hours, regardless of Bacillus Calmette-Guerin (BCG) or other vaccination history) or a positive (not indeterminate) TB test such as QuantiFERON®-TB Gold Plus test. NOTE: The choice to perform a TST or a QuantiFERON-TB Gold Plus test will be made by the investigator according to local licensing and standard of care. The QuantiFERON-TB Gold Plus test can only be used in countries where it is licensed, and the use of this test is dependent on previous treatment(s). This test may not be suitable if previous treatment(s) produced significant immunosuppression"	To align with Sanofi common text and safety guidance. To respond the FDA's comment to obtain Mantoux TST test prior to study enrollment.
	Introduced the history of serious infection or currently active infection (including COVID-19) as exclusion #24	To align with Sanofi common text and safety guidance.
	Introduced the receipt of COVID-19 vaccine as exclusion #25	To align with COVID-19 vaccine safety profile.
Section 1.3 SoA	Updated the assessment item from "Evaluation of BSA involvement" to "Evaluation of treatable BSA"	For clarity.
	Added FSH test and footnote f to clarify it is for post-menopausal women of non-childbearing potential only. Renumbered the footnote thereafter.	To align with Table 6.
	Added Urinalysis test.	To align with inclusion #10 and Table 6
	Removed the footnote b from PP- NRS assessment	To correct an error and be consistent within protocol.
	Day 15 has been included in footnote q of biomarker collection.	To correct an omission
	Revised the footnote i with "The vIGA-AD will be conducted on all treated lesions at screening and Day 15, 29 and 43 during Open Label period.	To clarify the vIGA-AD is for all treated lesions and the scheduled study visit.

Section # and Name	Description of Change	Brief Rationale
	Added "predose at Day 15" at the end of footnote j .	To correct an omission.
	Newly added footnote k "The lesional vIGA-AD will be administered predose separately on each of the 2 target lesions only during Blinded Period and predose at Day 15" and crossed link to Lesional vIGA assessment. Renumber the footnote thereafter.	To clarify the lesional vIGA-AD is only for 2 target lesions and the scheduled study visit.
Section 1.3 SoA, Section 8.9 lesion photography	Added "to document biopsy location and" for the purpose of photograph in footnote j and section 8.9.	For clarity.
Section 1.3 SoA, Table 6	Introduced the diagnostic assessments for Serology (HIV, hepatitis B and C) and TB test in screening visit.	To align with Sanofi common text and safety guidance. To respond the FDA's comment to obtain HIV test prior to study enrollment.
Section 4.1 overall design	Added the text clarifying study duration.	For clarity and align with synopsis.
Section 4.3 justification for dose	Added the following text "Patients will measure the dose by the fingertip unit method and the expected dose variability when the compound is topically self-applied by this method may be up to two-fold excess of compound which is reasonably below the safety margin."	To introduce the guidance for patient self-administration of study intervention in open-label period.
Section 4.4 end of study definition	Updated the definition for patient completed the study to "A patient is considered to have completed the study if he/she has completed all phases of the study including the Day 43 and Day 56 safety follow up phone call."	For clarity.
Section 6.7.1 COVID-19 vaccination	Introduced a new section for the guidance and requirements of use COVID-19 vaccination.	To clarify the guidance of COVID-19 vaccination during study in the context of its approval.
Section 6.7.2 prohibited medications, Table 5	Added any live vaccines in excluded medications and treatments list.	To align with vaccine safety profile.
Section 6.7.4 rescue medicine	Updated the text to "Rescue topical medications use will be at the discretion of the Investigator after discussion with the Medical Monitor if the patient is flaring above 14% treatable BSA (excluding scalp, palms, soles and genitalia) during the last two weeks of the Open Label Period. Investigators should make every attempt to conduct efficacy and safety assessments (eg, disease	To respond the FDA's comment to provide a plan for patients who flare and have >14% treatable BSA during the open label period.

severity scores, safety labs) immediately before administering any rescue treatment. An unscheduled visit may be used for this, if necessary. Patients who receive rescue treatment will be asked to continue with study treatment and procedures."	
Section has been updated to include subject stopping criteria based on liver chemistry and ECG abnormalities. In addition, introduced a new sub-section 7.1.4 for hematology stopping criteria.	To align with Sanofi common text and safety guidance.
Added the following text "Refer to Section 7.1.3 for QTc withdrawal criteria and any additional QTc readings that may be necessary."	For clarity. To respond the FDA's comment to add subject stopping criteria based on ECG abnormalities.
Corrected the clinical chemistry assessment from "Urate/Urea" to "Blood urea nitrogen (BUN)"	For clarity.
Added "Details of liver chemistry stopping criteria and required actions and follow-up are given in Section 7.1.2 Liver Chemistry Stopping Criteria and Appendix 5 Liver and other safety: suggested actions and follow-up assessments. All events which may indicate severe liver injury (possible Hy's Law) must be reported to Sponsor in an expedited manner (excluding studies of hepatic impairment or cirrhosis)." as footnote a and renumbered the following footnotes.	To align with Sanofi common text and safety guidance. To respond the FDA's comment to add subject stopping criteria based on liver chemistry.
Whole section been updated.	To align with Sanofi common text and safety guidance.
Included the regulatory requirement of reporting SUSAR as one of the listed bullet points.	To align with Sanofi common text and safety guidance.
Added the time window for expedited reporting of AE.	To align with Sanofi common text and safety guidance.
	rescue treatment. An unscheduled visit may be used for this, if necessary. Patients who receive rescue treatment will be asked to continue with study treatment and procedures." Section has been updated to include subject stopping criteria based on liver chemistry and ECG abnormalities. In addition, introduced a new sub-section 7.1.4 for hematology stopping criteria. Added the following text "Refer to Section 7.1.3 for QTc withdrawal criteria and any additional QTc readings that may be necessary." Corrected the clinical chemistry assessment from "Urate/Urea" to "Blood urea nitrogen (BUN)" Added "Details of liver chemistry stopping criteria and required actions and follow-up are given in Section 7.1.2 Liver Chemistry Stopping Criteria and Appendix 5 Liver and other safety: suggested actions and follow-up assessments. All events which may indicate severe liver injury (possible Hy's Law) must be reported to Sponsor in an expedited manner (excluding studies of hepatic impairment or cirrhosis)." as footnote a and renumbered the following footnotes. Whole section been updated. Included the regulatory requirement of reporting SUSAR as one of the listed bullet points.

Section # and Name	Description of Change	Brief Rationale
Section 9.4.3 analysis of efficacy data	Included the following text "Where appropriate, supplemental analyses will be presented excluding observations after administration of rescue medication. Imputation would then be performed for missing observations including those due to withdrawal due to lack of efficacy, as will be specified in the SAP."	To include efficacy data after the use of rescue medication.
Section 9.4.4 analysis of safety data	Included the following text "Where appropriate, supplemental analyses will be presented excluding observations after administration of rescue medication."	To include safety data after the use of rescue medication.
Section 10 supporting documentation and operational considerations	Added a new subsection 10.1.7.1 for trial stopping rules in Appendix 1	To align with Sanofi common text and safety guidance.
	Included the contraceptive and barrier guidance, laboratory decision trees for neutropenia and thrombocytopenia as Appendix 2.	To align with Sanofi common text and safety guidance.
	Included neutropenia and thrombocytopenia decision trees in Appendix 3	To align with Sanofi common text and safety guidance.
	Grouped the original appendices 1 to 4 as the subsection of Appendix 4 of additional appendices.	For clarity.
	Protocol amendment history added as Appendix 5 per Sanofi template.	Administrative update.
Throughout document	Replaced "study drug" with "study intervention".	To align with Sanofi protocol template terminology recommendation.
Throughout document	Other minor editorial changes (eg, grammatical, stylistic, and minor typographical error corrections)	Minor, therefore, have not been summarized

1 INTRODUCTION

1.1 STUDY DESIGN

PRN473 is also known as SAR444727 and both terminologies are used in an interchangeable way in this document. For the reporting “SAR444727” will be used.

Study ACT17131 is a Phase 2a that consists of a randomized, double-blind, intra-patient placebo-controlled treatment period and an open-label uncontrolled treatment period.

The objective of the study is to evaluate the safety, tolerability, pharmacokinetics (PK) and preliminary efficacy of topically administered SAR444727 in up to 40 participants with mild to moderate atopic dermatitis (AD).

On Day 1 (Baseline) of the Blinded Period, 2 target lesions of 100 cm² area each with a difference no greater than 1 point in lesional Total Sign Score (TSS) are randomly assigned to treatment in an intra-participant 1:1 manner, with one lesion assigned to SAR444727 Gel 5% and the other to matching placebo (ie, same inactive ingredients). SAR444727 Gel 5% and matching placebo (ie, same inactive ingredients) are applied twice a day (BID, morning and evening) at a quantity of 2.5 mg/cm² to a 100 cm² area of each target lesion on Days 1-14 (Blinded Period). On Days 15-42 (Open-Label Period), participants are instructed to apply SAR444727 Gel, 5% BID to all AD-affected areas in a thin layer (excluding the scalp, palms, soles and genitals), and should continue to treat the assigned areas throughout the Open-label Period.

Participation will take approximately 13 weeks, including up to a 5-week screening period, a 6-week treatment period (2-week blinded and 4-week open label), end of study assessments 1 day after last dose, and a safety follow-up phone call 2 weeks after last dose.

1.2 OBJECTIVE AND ENDPOINTS

Table 1 - Objectives and endpoints

Objectives	Endpoints
Primary	
Safety: To assess the safety and tolerability of PRN473 Gel, 5% versus placebo administered BID up to 6 weeks in participants with mild to moderate AD	Safety: 
Incidence and severity of AEsChanges in vital signs, ECGs, and laboratory testsAssessment of local cutaneous tolerability: incidence and severity of application-site events such as burning/stinging, itching, and erythema
PK: To evaluate the plasma PK of PRN473 following administration of multiple topical doses of PRN473 Gel, 5% for 42 days in participants with mild to moderate AD	
PK: Plasma PRN473 concentrations at specified timepoints

Objectives	Endpoints

Exploratory
 
 Biomarker: To evaluate blood and skin changes in protein expression, lymphocyte infiltration, and epidermal thickness following treatment with PRN473 Gel, 5% at Days 8 and 15 Efficacy: To assess the preliminary efficacy following double-blind treatment with PRN473 Gel, 5% compared to placebo at Days 8 and 15 Efficacy: To assess the preliminary efficacy following open-label treatment with PRN473 Gel, 5% at Days 29 and 43 	
 Biomarker: Change from Baseline in biomarkers using blood samples, skin tape stripping, and skin biopsy 
Efficacy During Blinded Period:
 
 Change from Baseline in lesion TSS at Days 8 and 15 Change from Baseline in daily lesional PP-NRS score up to Day 15 Change from Baseline in lesional validated IGA score at Days 8 and 15 Lesional validated IGA response (proportion of participants with a validated IGA score of 0 or 1 and ≥ 2-grade improvement from Baseline) at Days 8 and 15 
Efficacy During Open-Label Period
 
 Change from Baseline in TSS for the 2 target lesions at Days 29 and 43. 
For EASI:
 
 Percent change from Baseline in EASI at Days 29 and 43 Percent change from Day 15 in EASI to Days 29 and 43 Proportion of patients with EASI 50, EASI 75, and EASI 90 from Day 15 to Days 29 and 43 
For PP-NRS:
 
 Change in PP-NRS from Day 15 to Days 29 and 43 Proportion of participants achieving at least 3-point reduction from Day 15 in PP-NRS at Days 29 and 43 Proportion of participants achieving at least a 4-point reduction from Day 15 in PP-NRS at Days 29 and 43 Change from Day 15 in weekly mean of PP-NRS at Days 29 and 43 
For vIGA-AD:
 
 Proportion of participants achieving at least 2 grade reduction in vIGA-AD to clear (vIGA-AD 0) or almost clear (vIGA-AD 1) from Day 15 to Days 29 and 43 
Other endpoints:
 
 Change from Day 15 in SCORAD at Days 29 and 43 Change from Day 15 in percentage of treatable BSA at Days 29 and 43 Change from Baseline in POEM at Days 15, 29, and 43 Proportions of participants with a reduction in POEM ≥ 4 from Baseline at Days 15, 29 and 43 in participants with POEM ≥ 4 at Baseline Proportions of participants with a reduction in POEM ≥ 4 from Day 15 at Days 29 and 43 in participants with POEM ≥ 4 at Baseline Change from Baseline in DLQI at Days 15, 29, and 43

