5.1 INCLUSION CRITERIA

Patients are eligible to be included in the study only if all the following criteria are met:

- 1. Male and female adults 18 to 70 years of age (inclusive) at the time of informed consent.
- 2. Diagnosed with mild to moderate AD, meeting at least 3 major and 3 minor criteria according to Hanifin and Rajka (Hanifin 1980; Appendix 4, Section 10.4.4) prior to or at the Screening visit.
- 3. History of AD for at least 6 months as determined by the Investigator through patient interview.
- 4. Stable disease for the 4 weeks prior to the screening visit with no significant flares in AD as determined by the Investigator.
- 5. Validated Investigator Global Assessment-atopic dermatitis (vIGA-AD) score of Moderate (3) or Mild (2) at Screening. The vIGA-AD is evaluated for the entire body except scalp, palms, soles and genitals.
- 6. Has AD involvement (excluding scalp, palms, soles and genitals) of at least 1.0% BSA and no more than 14.0% BSA.
- 7. Has at least two target lesions 100 cm² or greater with a difference no greater than 1 point in lesion TSS and at least 5 cm apart located on the trunk (excluding genitals) or upper extremities (excluding palms)
- 8. Male patients are eligible to participate if they agree to the following during the intervention period and for at least 2 days (eg, 5 terminal half-lives) after the last dose of study intervention,
- Refrain from donating sperm

PLUS, either:

- Be abstinent from heterosexual intercourse as their preferred and usual lifestyle (abstinent on a long term and persistent basis) and agree to remain abstinent.

OR

Must agree to use contraception/barrier as detailed below:
 Agree to use a male condom and an additional highly effective contraceptive method as described in Appendix 2 Contraceptive and barrier guidance (Section 10.2) when

having sexual intercourse with a woman of childbearing potential (WOCBP) who is not currently pregnant.

- 9. A female patient is eligible to participate if she is not pregnant or breastfeeding, and one of the following conditions applies:
- Is a WONCBP as defined in Appendix 2 Contraceptive and barrier guidance (Section 10.2).

OR

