3.4 TERTIARY/EXPLORATORY ENDPOINT(S) ANALYSIS

There are two type of exploratory endpoints. The first exploratory endpoint is biomarker to evaluate changes in blood samples, skin tape stripplings, and skin biopsies. Details are given in [Section 3.7.1.2](#).

The second exploratory endpoints are efficacy endpoints during double-blind period and Open-label period based on the efficacy population. For the double-blind period, treatment differences or ratios will be assessed for SAR444727 Gel, 5% versus placebo at Day 8 and Day 15, and data will be presented by treatment for the blinded period, for scores assessed per lesion, and overall otherwise. During the Open-Label Period, efficacy will be assessed mainly at Days 29 and 43,

overall. For TSS, data will be described over the full course of the study presented by treatment received during the double-blind Period.

More specifically, the following endpoints will be assessed:

During double-blind period

- Change from Baseline in lesional TSS for the 2 target lesions at Day 8 and Day 15
- Change from Baseline in daily lesional Peak Pruritus Numeric Rating Scale (PP-NRS) score for the 2 target lesions up to Day 15 and at Day 15
- Change from Baseline in lesional validated Investigator Global Assessment for AD (v-IGA-AD) score for the 2 target lesions at Days 8 and 15
- Lesional v-IGA-AD response (proportion of participants with a lesional v-IGA-AD score of 0 [clear] or 1 [almost clear] and ≥ 2 -grade improvement from Baseline) at Days 8 and 15

During Open-label period

- For lesional TSS
 - Change from Baseline in lesional TSS for the 2 target lesions at Days 29 and 43
 - Change from Day 15 in lesional TSS for the 2 target lesions at Days 29 and 43
- For PP-NRS
 - Change in daily global PP-NRS from Day 15 to Days 29 and 43
 - Change in weekly average of PP-NRS from Day 15 to Days 29 and 43
 - Proportion of participants achieving at least 3-point reduction from Day 15 in daily global PP-NRS at Days 29 and 43 in participants with PP-NRS ≥ 3 at Day 15
 - Proportion of participants achieving at least a 4-point reduction from Day 15 in daily global PP-NRS at Days 29 and 43 in participants with PP-NRS ≥ 4 at Day 15
- For Eczema Area and Skin Severity Index (EASI)
 - Percent change from Baseline in EASI at Days 29 and 43
 - Percent change from Day 15 in EASI at Days 29 and 43

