 - Proportion of participants with at least a reduction $\geq 50\%$ in EASI (EASI-50), with at least a reduction $\geq 75\%$ in EASI (EASI-75), with at least a reduction $\geq 90\%$ in EASI (EASI-90), and with at least a reduction $\geq 100\%$ in EASI (EASI-100), from Baseline to Days 15, 29 and 43
 - Proportion of participants with EASI-50, EASI-75, EASI-90, and EASI-100 from Day 15 to Days 29 and 43
- For v-IGA-AD
 - Proportion of participants achieving vIGA-AD of 0 (clear) or 1 (almost clear) at Day 29

- Proportion of participants achieving a vIGA-AD of 0 (clear) or 1 (almost clear) at Day 43
- Proportion of participants achieving vIGA-AD of 0 (clear) or 1 (almost clear) and a reduction of ≥ 2 points from Day 15 to Day 29
- Proportion of participants achieving vIGA-AD of 0 (clear) or 1 (almost clear) and a reduction of ≥ 2 points from Day 15 to Day 43
- For Body Surface Area (BSA)
 - Change from Day 15 in percentage of treatable BSA at Days 29 and 43
- For Scoring Atopic Dermatitis (SCORAD)
 - Percent change from Day 15 in SCORAD index at Days 29 and 43
- For Patient Oriented Eczema Measure (POEM)
 - Change from Baseline in POEM at Days 15, 29, and 43
 - Change from Day 15 in POEM at Days 29 and 43
 - Proportions of participants with a reduction in POEM ≥ 4 from Baseline at Days 15, 29 and 43 in participants with POEM ≥ 4 at Baseline
 - Proportions of participants with a reduction in POEM ≥ 4 from Day 15 at Days 29 and 43 in participants with POEM ≥ 4 at Day 15
- For Dermatology Quality of Life Index (DLQI)
 - Change from Baseline in DLQI at Days 15, 29, and 43.
 - Change from Day 15 in DLQI at Days 15, 29, and 43
 - Proportions of participants with a reduction in DLQI ≥ 4 from Baseline at Days 15, 29 and 43 in participants with DLQI ≥ 4 at Baseline
 - Proportions of participants with a reduction in DLQI ≥ 4 from Day 15 at Days 29 and 43 in participants with DLQI ≥ 4 at Day 15

Analyses for binary endpoints

The binary endpoints will be descriptively summarized using number, percentage and 95% confidence interval (CI) of percentage at each time point.

The proportion of subjects meeting the binary endpoint during the Open label period and corresponding exact 95% and 80% CI (95% CI and 80% CI respectively calculate with Wilson score method) will be summarized.

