Participants with missing data at Baseline will not be included in the analysis. Participants with one or more post-dose timepoints will be included. Mixed model for repeated measures (MMRM) to account for missing data is used for the primary analysis under the missing at random (MAR) framework. Parameters will be estimated using restricted maximum likelihood method with the Newton-Raphson algorithm. Denominator degrees of freedom will be estimated using Kenward-Roger adjustment. All efficacy data after discontinuation of treatment will not be considered.

The same analysis will be conducted for lesional v-IGA-AD score at Days 8 and 15 and lesional PP-NRS. For the other efficacy parameters, only descriptive analyses will be provided.

The weekly average PP-NRS scores will be defined as the average of daily non-missing scores within the week preceding the given visit and will be calculated if there is a minimal amount of 4 non-missing scores.

The POEM score is a 5-point scale: 0 (“No days”), 1 (“1-2 days”), 2 (“3-4 days”), 3 (“5-6 days”) and 4 (“Every day”). The POEM score is calculated by summing the values for the 7 items.

If two or more questions are left unanswered the questionnaire is not scored.

The DLQI is a 4-point scale: 0 (“Not relevant”/“Not at all”), 1 (“A little”), 2 (“A lot”), 3 (“Very much”). For Question 7, “Prevented work or studying” is scored at 3. The DLQI is calculated by summing the score of each question.

The EASI-50/75/95/100 response is defined as a participant achieved a decrease by at least 50%/ 75%/ 95%/100% of EASI from Day 15.

Change in lesional TSS, PP-NRS (daily global and weekly average), EASI, BSA, SCORAD, POEM, DLQI during the Open label period will be analyzed descriptively. Estimations with 95% and 80% CIs may be derived. Sub-score of EASI by localization will also be provided.

Supplemental analyses

Where appropriate, supplemental analyses may be presented excluding observations after administration of rescue medication. No imputation will be made.

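### SAP Table 1 restricts the POEM response from Day 15 on the Baseline score, while SAP Section 3.4 restricts the same endpoint on the Day 15 score

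*SAP*

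**What the plan says.** SAP Section 1.2, Table 1, lists the POEM response measured from Day 15 as "from Day 15 at Days 29 and 43 in participants with POEM ≥ 4 at Baseline". SAP Section 3.4 lists the same 4-point reduction, from the same reference visit and at the same two visits, as "from Day 15 at Days 29 and 43 in participants with POEM ≥ 4 at Day 15". The run that the two entries share, "from Day 15 at Days 29 and 43 in participants with POEM", leads to a different qualifying visit in each place: Baseline in Table 1 and Day 15 in Section 3.4.

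On scoring, Section 3.4 gives each item a value from 0 to 4 and states: "The POEM score is calculated by summing the values for the 7 items".

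The neighbouring responders in Section 3.4 follow one rule: the score that qualifies a participant is taken at the visit from which change is measured. The PP-NRS responders, measured from Day 15, are assessed "at Days 29 and 43 in participants with PP-NRS" of at least 3 or at least 4 at Day 15. The DLQI responders are restricted at Baseline when change is from Baseline, and at Day 15 when change is from Day 15.

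Nothing else in the documents settles the difference. The protocol (Section 3, Table 3) has only the mean change in POEM from Baseline and no POEM responder. SAP Section 3.9 lists only changes to the analysis populations. The SAP is version 1, so neither wording is superseded text.

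**The concern.** A responder percentage is only as clear as its denominator. Table 1 qualifies participants on a score taken at a different visit from the one where their change starts. Some participants who improved during the Blinded Period could then be counted as open-label non-responders although the scale leaves them no room to respond. Others, who worsened to a score from which they could respond, would be left out.

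The Open-Label Period has no comparator, so the percentage and its interval are the whole result, and nothing in a control arm offsets a wrong denominator. SAP Section 3.8 also allows open-label data into the interim analysis, under the same SAP conventions, so the ambiguity could arise there too.

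**Working it through.** The plan states no response rate or sample size calculation, so there is no figure to reproduce. The check is which participants each wording admits, followed by an illustration.

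**Who can respond.** The range is 7 items × 0 to 4 = 0 to 28. A fall of at least 4 needs a Day 15 score of at least 4. Scores of 4 to 28 can respond; scores of 0 to 3 cannot.

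**Who is counted.** Classify participants by the two scores:

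| Group | Baseline | Day 15 | Can respond? | Table 1 | Section 3.4 |
|---|---|---|---|---|---|
| a | ≥4 | ≥4 | yes | in | in |
| b | ≥4 | 0–3 | no | in | out |
| c | 0–3 | ≥4 | yes | out | in |
| d | 0–3 | 0–3 | no | out | out |

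Let x_a and x_c be the responders in groups a and c.

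- Table 1 rate = x_a / (a + b), with a maximum of a / (a + b).
- Section 3.4 rate = (x_a + x_c) / (a + c), with a maximum of 100%.
- Difference in denominators = b − c, which may have either sign.

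**Illustration 1: c = 0.** Assumptions: 40 participants (the planned maximum), all with Baseline POEM ≥4, b of them at 0 to 3 on Day 15, and half of the rest responding. Intervals are Wilson 95%, the method named in Section 3.4: centre (p + z²/2n)/(1 + z²/n), half-width z√(p(1−p)/n + z²/4n²)/(1 + z²/n), z = 1.96.

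| b | Section 3.4 | Table 1 | Table 1 maximum |
|---|---|---|---|
| 4 | 18/36 = 50.0% (34.5–65.5) | 18/40 = 45.0% (30.7–60.2) | 90% |
| 8 | 16/32 = 50.0% (33.6–66.4) | 16/40 = 40.0% (26.3–55.4) | 80% |
| 12 | 14/28 = 50.0% (32.6–67.4) | 14/40 = 35.0% (22.1–50.5) | 70% |

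With a response rate near 30% and b = 8, the pair is 10/32 = 31.3% (18.0–48.6) and 10/40 = 25.0% (14.2–40.2).

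**Illustration 2: c > 0.** Assume a = 32, b = 4, c = 4, with half of a and half of c responding. Both denominators are 36, but Table 1 gives 16/36 = 44.4% and Section 3.4 gives (16 + 2)/36 = 50.0%. Equal denominators do not mean the same participants.

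**Direction.** With a = 32, b = 0, c = 4, and responders 16 in a and none in c, Table 1 gives 16/32 = 50.0% and Section 3.4 gives 16/36 = 44.4%. Table 1 is therefore not always the lower figure.

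**The case against.** The best defence is that Section 3.4 plainly governs. It is the analysis section, it introduces its list as the more specific one, and its POEM rule is coherent. Table 1 is the shorter list of objectives; its PP-NRS responders carry no restriction at all, and Section 3.4 adds one. A programmer working from Section 3.4 would count no participant who is unable to respond. This stands in part: Section 3.4 is probably what was meant, and the two percentages arise only if someone follows Table 1. But for POEM, Table 1 is not merely shorter. It states a restriction, and a different one. The SAP does not say which section prevails.

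A second defence is that little depends on it. The endpoint is exploratory, the sample is at most 40, no hypothesis is tested, and the intervals above overlap heavily. That also stands, and it limits the point to a correction of wording.

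A reader might also infer that the vIGA-AD 2-grade response has the same fault, because a Day 15 score of 0 or 1 cannot fall two grades. The documents do not support calling that an error. Table 1 has "Proportion of participants achieving at least 2 grade reduction in vIGA-AD to clear (vIGA-AD 0) or almost clear (vIGA-AD 1) from Day 15", assessed at both later visits. Section 3.4 has "Proportion of participants achieving vIGA-AD of 0 (clear) or 1 (almost clear) and a reduction of" at least 2 points from Day 15. Protocol Sections 1.1, 3 and 9.4.3.4 agree, and none restricts on Day 15. An all-participant denominator is a legitimate definition of response. Section 3.4 also plans the plain proportion at 0 or 1 at Days 29 and 43, where a participant who is clear at Day 15 and stays clear counts as a success.

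Nor do the documents show how many would be at 0 or 1 on Day 15. Entry requires a "score of Moderate (3) or Mild (2) at Screening". At the protocol's reference body surface of 1.9 m², the 1.0% minimum involvement is 190 cm², against 2 × 100 cm² treated in the Blinded Period, one area with placebo. At the 14.0% maximum, involvement is 0.14 × 19,000 = 2,660 cm². Such scores are possible, but no frequency follows.

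**Conclusion.** The POEM conflict is real and the Table 1 wording is wrong as it stands: it admits participants who cannot respond and excludes some who can. Section 3.4 has neither fault and matches the reference-visit rule used there for PP-NRS and DLQI.

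The effect is confined to one exploratory, descriptive, uncontrolled percentage and its interval. No error rate or power is involved. The sizes in the working rest on assumed group counts and response rates. The documents do not give the number affected, whether the denominator grows or shrinks, or which wording gives the higher rate.

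The point does not extend to vIGA-AD. Restricting that response would be a preference for a different summary, not the repair of an inconsistency.

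**What to change.** In SAP Section 1.2, Table 1, change the qualifying visit for the POEM response from Day 15 so that it reads POEM ≥4 at Day 15, in agreement with Section 3.4. Leave the companion POEM response from Baseline restricted at Baseline, which is already right.

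The cost is one phrase. It needs no new data, no new visit and no protocol change, since the protocol has no POEM responder. Relative to Table 1 as written, the denominator may rise or fall.

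Optionally, the vIGA-AD 2-grade response could also be shown among participants with Day 15 vIGA-AD ≥2 as a supplementary summary, beside the definition already planned and not in place of it. A score of 2 can still respond, but only by reaching 0, and a footnote should say so.
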